3 ABBREVIATIONS

Abbreviation	Term
6MWT	6-minute walk test
AE	adverse event
COPD	chronic obstructive pulmonary (lung) disease
CRF	Case report form
FEV1	forced expiratory volume in the 1st second of the FVC maneuver
FVC	forced vital capacity
GCP	Good Clinical Practice
ICH	International Conference on Harmonization
IEC	Independent Ethics Committee
IMT	Inspiratory muscle training
MEP	maximal expiratory pressure
MIP	maximal inspiratory pressure
pCRF	paper case report form
PFT	pulmonary function test
RMT	Respiratory Muscle Training
SAE	serious adverse event
FDSS	Fatigue Daytime Sleepiness Scale
DM1-Activ	Rasch-built myotonic dystrophy type 1 activity and participation scale
BGA	Blood gas analysis

4 INTRODUCTION

Myotonic dystrophy type 1 (DM1, Myotonia congenita Curschmann-Steinert) is an autosomal dominant transmitted, rare, progeroid disease with slow progression (Bird 1993, Mateos-Aierdi, Goicoechea et al. 2015). With a prevalence of 10/100,000, it is the most common muscular dystrophy in adulthood (Norman, Floyd et al. 1989, Norwood, Harling et al. 2009). According to current knowledge, the expansion of the CTG trinucleotide repeat on chromosome 19q13.3 leads to an accumulation of transcription aggregates in the cell nuclei, which indirectly influences the RNA metabolism. The length of this expansion influences both the age of onset of the disease and the manifestation of the symptoms and thus the severity of the disease with increasing age (Meola 2013, Meola and Cardani 2015, Santoro, Masciullo et al. 2017). The different symptoms are currently best explained by incorrect splicing mechanisms in subordinated effector genes (Gladman, Mandal et al. 2013).

The clinical presentation of DM1 is very variable. The inconsistent combination of muscular and extramuscular symptoms often complicates early diagnosis and leads to an early reduction of quality of life, chronic disability, reduced ability to work and reduced life expectancy in affected patients. Leading muscle symptoms are myotonia, a slowly progressive and distal emphasized tetraparesis with reduced muscular endurance and performance, associated with muscular atrophy. The progressive muscle weakness includes not only the extremities, but also the trunk and respiratory muscles in various forms. In the majority of patients, respiratory muscle weakness leads to an early start of mechanical ventilation (Babacic, Goldina et al. 2018). A central respiratory regulation disorder, such as a central sleep apnea with concentration disorders, fatigue, headache and reduced physical and/or muscular endurance and performance, can appear in some of these patients as well (Boentert, Wenninger et al. 2017, Evangelista, Dias et al. 2017). Among high variability of extramuscular symptoms, neuropsychological symptoms such as chronic fatigue syndrome with excessive daytime sleepiness, depressive disorders, as well as reading and spelling difficulties have been observed (Stahl, Wenninger et al. 2016). These symptoms partly overlap with those of chronic respiratory insufficiency, with the consequence that diagnosis and therapy may be delayed (Boentert, Wenninger et al. 2017). Accordingly, recommendations for regular lung function diagnostics in patients with myotonic dystrophy and recently also a special questionnaire on symptoms of respiratory insufficiency were published (Sansone and Gagnon 2015). Cardiac (arrhythmia) and endocrine diseases (diabetes mellitus, thyroid metabolism), cataracts and gastrointestinal symptoms are regular accompanying symptoms. The combination of muscular and extramuscular symptoms leads to severe functional deficits, causing impaired quality of life at an early stage of the disease and may endanger the ability to work (Kierkegaard, Harms-Ringdahl et al. 2011, Laberge, Mathieu et al. 2013).

At the moment, there is no causal therapy for this autosomal dominant inherited disease, so the focus of patient care is on symptomatic therapy. Modafinil and Ritalin have long been used with moderate success in cases of excessive daytime sleepiness (Hilton-Jones, Bowler et al. 2012, Puymirat, Bouchard et al. 2012). High-frequency physiotherapy and occupational therapy can positively influence gripping function and thus self-sufficiency; an (intermittent) mechanical mask ventilation (NIV - non-invasive ventilation) is established with increasing restrictive ventilation disorder (Sansone and Gagnon 2015, Boentert, Wenninger et al. 2017); peripheral muscle relaxants or Mexiletin can reduce myotonia and pain caused by muscular

tension (Smith and Gutmann 2016); regular physical activity can decelerate the slowly progressing muscular degradation and prevent secondary complications - especially of joint function (Cup, Pieterse et al. 2007, Schilling, Forst et al. 2013, Voet, van der Kooi et al. 2013).

In contrast to other neuromuscular diseases with an early involvement of the respiratory muscles such as glycogen storage disease type II (Pompe disease) or Duchenne muscular dystrophy, there are no meaningful clinical studies for myotonic dystrophy type 1 that could prove a positive or negative effect of regular respiratory muscle training. On the other hand, it could be shown that early and regular respiratory muscle training can significantly improve inspiratory respiratory muscle strength and delay the onset of ventilation in Pompe's disease and Duchenne muscular dystrophy (Martin, Stern et al. 1986, Rodillo, Noble-Jamieson et al. 1989, Aslan, Gurses et al. 2014, Eidenberger and Nowotny 2014, Ferreira, Costa et al. 2016, Jones, Crisp et al. 2016, Human, Corten et al. 2017, Wenninger, Greckl et al. 2018). Only one case study from 2006 presented a lack of improvement of the symptoms of respiratory insufficiency after respiratory muscle training in one patient (de Freitas Fregonezi, Resqueti et al. 2006). Due to the lack of results from high-quality studies, respiratory muscle training has not yet been included in the current recommendations for patients with myotonic dystrophy type 1.

5 RISKS AND BENEFITS

5.1 Summary of Potential Risks

Study specific procedures and associated risks are bulleted below:

- Functional testing (six-minute-walk-test): falls, shortness of breath, muscle soreness, myalgia and fatigue
- Pulmonary function testing: dizziness, shortness of breath, discomfort
- Blood draws for oximetry: momentary discomfort, bruising, excessive bleeding, infection
- Respiratory muscle strength training: dizziness, myalgia of respiratory muscles, fatigue, shortness of breath, discomfort
- Respifit S®: Study results on respiratory muscle training in patients with the muscle disease M. Pompe ("Safety and efficacy of short- and long-term inspiratory muscle training in late-onset Pompe disease (LOPD): a pilot study". Wenninger S. et al (2018)) have provided no evidence that the use of the Respifit S device can cause relevant side effects or health risks so far.

5.2 Summary of Potential Benefits

Respiratory muscle training (RMT) is well known and established in patients with chronic obstructive lung disease (COPD) and can improve symptoms in these patients within four weeks of training (Borge, Hagen et al. 2014). While training, patients might improve their respiratory muscle function and symptoms related to respiratory insufficiency might vanish or improve. The quality of life, performance and fatigue may also improve. The need for (non-)invasive ventilation can also be reduced or delayed.

6 STUDY OBJECTIVES

The primary objective of this study is to determine the safety of repetitive respiratory muscle training on respiratory muscle strength as measured by MIP (maximum inspiratory pressure) in the upright position.

The secondary objectives are to evaluate the

- efficacy and safety of repetitive inspiratory strength respiratory muscle training in 15 patients with myotonic dystrophy type 1,
- efficacy and safety of repetitive inspiratory endurance respiratory muscle training in 15 patients with myotonic dystrophy type 1,
- Measurement of the effect on the quality of life and muscular performance in patients with myotonic dystrophy type 1 during respiratory muscle training or in patients without respiratory muscle training, using the questionnaires "DM1-Activ", "Respicheck" and "FDSS-Fatigue and Daytime Sleepiness-Scale",
- Measurement of the effect on the values CO₂ and O₂ in capillary blood gas analysis of patients with myotonic dystrophy type 1 during respiratory muscle training or in patients without respiratory muscle training,
- Measurement of the effect on muscular endurance performance in patients with myotonic dystrophy type 1 during respiratory muscle training or in patients without respiratory muscle training, measured by the 6-minute walking test.

7 INVESTIGATIONAL PLAN

This is a monocentric, three-arm, controlled interventional study for patients with myotonic dystrophy type 1. The patient is not blinded regarding his group assignment (group 1 and 2: respiratory muscle therapy, group 3 control group without respiratory muscle therapy). The patient must provide signed informed consent prior to the study. Suitable patients will either perform

- (a) A nine-month strength training of respiratory muscles (group 1: strength training); or
- (b) A nine-month endurance training of the respiratory muscles (group 2: endurance training);
- (c) Or will not perform any respiratory muscle training for nine months (Group 3: control group).

Lung function tests (FVC, FEV1, MIP, MEP), capillary blood gas analysis (pO₂, pCO₂), 6-minute walking tests, oxygen saturation, and patient questionnaires on quality of life and respiratory symptoms are performed on scheduled visits throughout the entire treatment period. Adverse events (AE) and concomitant medication / therapies will continuously be monitored throughout the whole study. Patients who must be excluded from the trial for safety reasons or who withdraw their participation will not be replaced (i.e. a patient's study number will not be reused); however, it is planned to recruit additional patients if patients terminate participation prematurely.

7.1 Discussion of study design, including choice of control group

This is a monocentric, three-arm, controlled interventional study for patients with myotonic dystrophy type 1. The patient is not blinded regarding his group assignment (group 1 and 2:

respiratory muscle therapy, group 3 control group without respiratory muscle therapy). The efficacy and safety of regular training of the respiratory muscle on the patient's health status is to be investigated.

The endpoints for this study are changes from baseline to month 9 after repetitive training.

7.2 End Points

7.2.1 Safety end points

Routine safety assessments are considered as primary endpoints of this study and are described in the sections 8, 9, 10 and 11.

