1 SYNOPSIS

TITLE: DMIMT - Controlled, randomized, three-arm interventional study on safety and efficacy of regular respiratory muscle training in patients with myotonic dystrophy type 1
PROTOCOL-NUMBER: Version 1.2 (26. June 2019)
STUDY CENTRE/CLINIC/INSTITUE: Friedrich-Baur-Institute, Klinikum der Universität München, [name], Germany
OUTCOME MEASURE: The primary objective of this study is to investigate the safety of repetitive respiratory muscle training on respiratory muscle strength measured by MIP (maximum inspiratory pressure) in the upright position. The secondary objectives are 
• Efficacy and safety of repetitive inspiratory strength muscle training in 15 patients with myotonic dystrophy type 1,• Efficacy and safety of repetitive inspiratory endurance muscle training in 15 patients with myotonic dystrophy type 1,• Measurement of the effect on the quality of life and muscular performance in patients with myotonic dystrophy type 1 during respiratory muscle training or in patients without respiratory muscle training, measured using the questionnaires "DM1-Activ", "Respicheck" and "FDSS-Fatigue and Daytime Sleepiness-Scale".• Measurement of the influence on CO₂ and O₂ values in capillary blood gas analysis of patients with myotonic dystrophy type 1 during respiratory muscle training or in patients without respiratory muscle training.• Measurement of the impact of respiratory muscle training on the 6-minute walking test in patients with DM1.

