7.2.2 Efficacy end points

Efficacy assessments are not considered to be primary endpoints of this study and are described in Section 8 and 10.

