8.3 Efficacy Assessments

The efficacy of training will be evaluated using results from lung function tests (FVC, FEV1, MIP, MEP), capillary blood gas analysis (pH, pCO₂, pO₂), functional assessments (6-minute walk test, oxygen saturation and Borg scale), and questionnaires on quality of life and symptoms of respiratory failure.

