8.4 Safety Assessments

Safety will be assessed for all enrolled patients from the time of signing the informed consent up to 7 days after the final study visit (month 9). Safety parameters include pulmonary function testing (PFT, including FVC, FEV1, MIP, MEP), physical examination, vital signs and –at decision of investigator- clinical laboratory tests as needed. See also Section 9.

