9 ADVERSE EVENTS REPORTING (AE)

A deterioration of >15% of FVC in comparison to baseline measurements will be defined as an AE, as well as developing unusual myalgia of respiratory muscles for more than 12 hours. AEs and SAEs will be coded using the Medical Dictionary for Regulatory Activities and summarized by primary system organ class and preferred term. Detailed listings of patients who experience AEs or SAEs will be presented. The incidence of treatment-emergent AEs and SAEs will be tabulated (frequencies and percentages) by severity, and by relationship to treatment. Adverse event severity will be categorized as mild, moderate, or severe. In tabulating severity of AEs on a per patient basis, the greatest severity will be assigned to a patient should there be more than one occurrence of the same AE with different reported severities. Relationships of the AE to treatment will be categorized as not related, unlikely related, possibly related, or related. The highest level of association will be reported in patients with differing relationships

for the same AE. Listings of AEs and SAEs for all patients will be provided, which will include severity and relationship to treatment, as well as actions taken regarding treatment, and patient outcome. A separate listing for patients who withdraw from the study due to AEs will be provided. The incidence of AEs leading to study discontinuations will also be summarized.

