10.6 Efficacy Analyses

Observed measurements and changes of the respiratory function parameters (FVC, FEV1 sitting and lying, MIP, MEP) up to the time of the study and health-related questionnaires on quality of life and symptoms of respiratory insufficiency are summarised using summary statistics. In addition, 95% confidence intervals will be used to estimate the change from baseline at each study visit. All data will be presented by study visit in by-patient listings.

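### The primary objective names upright MIP, but the endpoint sections make routine safety assessments as a group primary and class MIP as both safety and efficacy

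*Protocol*

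**What the plan says.** Five parts of the protocol bear on what is primary.

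- **Objective.** Section 6: "The primary objective of this study is to determine the safety of repetitive respiratory muscle training on respiratory muscle strength as measured by MIP", with the upright position specified. The synopsis says the same ("safety of repetitive respiratory muscle training on respiratory muscle strength measured by MIP").
- **Endpoints.** Section 7.2.1: "Routine safety assessments are considered as primary endpoints of this study", with a pointer to sections 8 to 11 and no variable named. Section 7.2.2: "Efficacy assessments are not considered to be primary endpoints of this study". Section 7.1 adds that endpoints are changes from baseline to month 9, again without naming a variable.
- **Assessments.** Section 8.3, on efficacy: "The efficacy of training will be evaluated using results from lung function tests (FVC, FEV1, MIP, MEP", followed by blood gases, the walk test and questionnaires. Section 8.4: "Safety parameters include pulmonary function testing (PFT, including FVC, FEV1, MIP, MEP), physical examination, vital signs", plus laboratory tests at the investigator's discretion.
- **Adverse events.** Section 9: "A deterioration of >15% of FVC in comparison to baseline measurements will be defined as an AE". The other specific trigger is unusual respiratory myalgia lasting more than 12 hours.
- **Analysis.** MIP appears only in the efficacy analyses. Section 10.6 begins "Observed measurements and changes of the respiratory function parameters (FVC, FEV1 sitting and lying, MIP, MEP" and plans 95% confidence intervals for change from baseline at each visit. The efficacy paragraph of the synopsis does the same.

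**The concern.** A primary endpoint should be the quantity that answers the primary objective. Here the objective names one variable, the endpoint section names an open group of assessments, and the named variable is analysed under the heading that section 7.2.2 declares non-primary. A reader of the final report could not tell from the protocol which result was meant to carry the safety conclusion.

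The stake is selective emphasis. The trial is open to patients, and lung-function manoeuvres depend on effort. If the lead safety result is not fixed, the report could open with MIP, with FVC or with adverse event counts, whichever looks best. A conclusion of safety could rest on few FVC events while MIP, the variable in the objective, appears only as a non-primary efficacy summary.

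This is not a detail that can be left to a statistical analysis plan. Such a plan can refine a definition, but it should not have to choose between conflicting statements in the protocol.

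**Working it through.** No arithmetic applies. The protocol gives no alpha, power, effect size or standard deviation, and 45 = 3 × 15 is a planned number with no calculation behind it. The check is to set the statements side by side.

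| Protocol section | Status given to MIP |
|---|---|
| Synopsis and 6 (objective) | The named measure for the primary objective |
| 7.2.1 with 8.4 | Primary, as one of several safety parameters |
| 7.2.2 with 8.3 | Efficacy, therefore not primary |
| 9 | Not used in either specific adverse event trigger |
| Synopsis (efficacy paragraph) and 10.6 | Summarised under efficacy only |

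1. **Status of MIP.** Combining 7.2.1 with 8.4 makes MIP primary. Combining 7.2.2 with 8.3 makes it not primary. Both chains follow from the text, so the protocol gives two answers.
2. **Whether 8.4 settles it.** It places MIP in the primary group beside FVC, FEV1, MEP, physical examination and vital signs. It does not single MIP out, as section 6 does, and it gives no time point or summary.
3. **Whether the analysis section settles it.** Section 10.7 covers physical examination and vital signs, and adverse events are tabulated under section 9. No part of section 10 analyses lung function as a safety outcome. The only MIP analysis is in 10.6, under efficacy, and it does not state the measuring position.
4. **Whether 7.1 settles it.** It fixes a time frame, baseline to month 9, but no variable. A change from baseline suits MIP or FVC. It does not suit adverse events, which have no baseline value.
5. **Whether the secondary objectives settle it.** They repeat efficacy and safety for each training arm, so safety is both a primary and a secondary objective.
6. **Whether one definition is feasible with the planned data.** In Appendix A, MIP is measured at months 0, 1, 3, 5, 7 and 9 in groups 1 and 2, and at months 0, 5 and 9 in group 3. Months 0, 5 and 9 are common to all groups, so a month-9 change against control needs no extra visit.

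**The case against.** The strongest reply is that this is a labelling fault. Section 7.2.1 sends the reader to section 8, and 8.4 names MIP as a safety parameter. Section 7.1 gives the time frame, and 10.6 produces the MIP change with a 95% confidence interval. One measure can serve safety (loss of strength) and efficacy (gain). The by-patient listings in sections 9 and 10.6 also mean that results are not hidden. Much of this stands, and it limits the point in three ways.

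- A reader might infer that the trial will have no primary MIP result at all. The documents do not support that: 7.2.1 with 8.4 puts MIP in the primary group, and its change will be reported.
- A reader might infer that safety on MIP cannot be judged because no adverse event trigger uses it. The FVC and myalgia rules define adverse events. They are not success criteria for an endpoint, and a descriptive study does not need a threshold for every measure.
- A reader might count the lung-function intervals over two training arms and quote a chance that at least one excludes zero. That treats descriptive intervals as tests, whereas sections 10.1 and 10.2 plan no formal tests and disclaim power for inference. It would also count false improvements as well as false losses, although only losses bear on safety. No error rate is claimed here.

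What the reply does not remove is the conflict between 7.2.1 and 7.2.2 over the one variable that the objective names. An exploratory study still has to say which result answers its primary objective, and listings do not prevent a later choice of emphasis.

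**Conclusion.** The protocol contradicts itself on its primary endpoint. MIP is the named measure in the objective, one of several primary parameters under one pair of sections, and non-primary under another. The consequence is an open choice of lead safety result in a trial where patients know their arm. It is not a lost result or an inflated error rate.

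The conclusion rests only on the text and on no assumed figure. It should be fixed before results are reported. It does not make the study invalid, because the design is an exploratory pilot and no sample size or test depends on the definition.

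**What to change.** State one primary definition and use it in the synopsis and in sections 6, 7.1, 7.2.1, 7.2.2, 8.3, 8.4 and 10.6.

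- Following the protocol's own objective and month-9 time frame, name change in upright MIP from baseline to month 9 as the primary safety variable. Report it for each training arm minus control with a 95% confidence interval, preferably adjusted for baseline MIP.
- State that it is read as a safety measure, so that the lower limit shows how much loss of strength the data can exclude. Any efficacy reading of MIP is then secondary.
- Keep adverse events explicitly within the primary safety evaluation, with the existing FVC and myalgia definitions unchanged. Moving them out would override 7.2.1.
- Label the other lung-function, blood gas, walk-test and questionnaire results secondary, and say where physical examination and vital signs belong.

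Another way to remove the contradiction is to keep the whole safety group primary and reword the objective. That is also consistent, but it gives up the single variable that the synopsis and section 6 chose, and it leaves the lead result open.

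The cost is a protocol amendment. Section 11.2 requires endpoint changes to be documented, signed by the investigator and approved by the ethics committee before use. No new data or visits are needed.

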7.2.2 Efficacy end points

Efficacy assessments are not considered to be primary endpoints of this study and are described in Section 8 and 10.

7.2.3 Completion of a patient's participation in the study

The length of a patient's participation will be from the time the informed consent form is signed until last planned assessment/visit and will be 9 months + 7 days follow-up period. A patient will be considered "completed" when the visit month 9 has occurred successfully according to the protocol.

